PRogram In Support of Moms: An Innovative Stepped-Care Approach for Obstetrics and Gynecology Clinics (PRISM)

NCT02760004

Document Date:5/9/23

Analysis plan

Our general approach to statistical analysis followed commonly accepted procedures. All analyses were conducted using SAS 9.4. As a first step in analysis, descriptive statistics and measures of association including measures of central tendency and measures of dispersion were used to summarize all variables. This analysis included graphical analysis of distributional characteristics of all variables. Bivariate associations between explanatory variables of interest were assessed by student t-tests, Wilcoxon rank-sum, and Chi-square tests for continuous, ordinal, and categorical values, respectively.

Data analysis Hypothesis 1. *Depressed perinatal patients receiving care from clinics enrolled in PRISM will experience more improvement in depression symptoms than patients receiving care from the enhanced usual care clinics (2 point difference-of-difference in EPDS)* To answer the specific hypothesis included in this difference-in-differences analysis aim we used unadjusted repeated measures linear regression models with the EPDS score as the dependent variable and the group (PRISM/MCPAP for Moms) and two time periods as the independent variables along with the interaction term of group by time period. The estimates of the difference in time points between groups was reported along with 95% confidence intervals (CI), p-values and the sample size (n).

Data analysis Hypothesis 2. *Depressed perinatal patients receiving care from clinics enrolled in PRISM will have improved treatment initiation and sustainment (as measured by attendance and one initial mental health assessment or treatment visit and an average ≥ 1 mental health visit every 1 months until remission of symptoms or study assessment) as compared to women receiving care from clinics enrolled in enhanced usual care.* Our primary outcome in this hypothesis was treatment initiation and sustainment, which was operationalized as receipt of prescription by an obstetrician, attendance in mental health visit(s), and adherence to medication, all of which were represented as dichotomous variables. Specifically, we used logistic regression to calculate odds ratios, corresponding confidence intervals and p-values to determine the impact of treatment group (PRISM/MCPAP) on treatment initiation and sustainment. These models were run both unadjusted and accounting for clustering of practices within treatment groups using Mixed Model analysis with clinic as a random effect.

Sub-hypothesis. *Depressed women receiving care from the enhanced usual care clinics will experience a small amount of improvement in depression and treatment participation at 12 months postpartum as compared to during pregnancy or immediately postpartum.* We anticipated that the enhanced usual care clinic will also experience improvement in both depression and treatment participation. As such we repeated the analyses outlined in H1 and H2 specifically within each of the treatment arms. In this instance, however, instead of considering a treatment by time interaction we only evaluated the time effect.

Additional analyses. A number of additional analyses are planned that will examine changes in patient level measures, as well as heterogeneity of the treatment effect, and will enable us to better understand how the intervention works and whether it works better for certain subset populations. We will examine the impact of gestational age or length postpartum on EPDS score. Additionally, we will test for both moderation and mediation. Specifically, we expect to conduct subgroup analysis by race/ethnicity, SES, psychiatric comorbidity, and practice type. To identify potential mediators we will use the classic method of mediation analysis as outlined by Baron and Kenny.¹²⁶ Mediation analysis seeks to understand the mechanisms through which the intervention has its effect. Therefore, measure of treatment fidelity and implementation are potential key mediators. To formally test for mediation we will use a technique developed by Karlson, Holm, and Breen,¹²⁷⁻¹²⁹ which decomposes the association of an independent variable with a given outcome into a direct and indirect (mediated) component in the context of a generalized linear model. This type of analysis will directly inform the dissemination plan by clueing us into which components of this multi-faceted intervention are responsible for substantial portions of observed effectiveness.

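### Does leaving perinatal stage out of the Hypothesis 1 model make the 2-point EPDS contrast misleading?

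*SAP*

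**What the plan says.** Under Data analysis Hypothesis 1, the SAP sets a target stated as "2 point difference-of-difference in EPDS" and gives one model: "To answer the specific hypothesis included in this difference-in-differences analysis aim we used unadjusted repeated measures linear regression models". The outcome is the EPDS score. The explanatory terms are the group and "two time periods as the independent variables along with the interaction term of group by time period". The section does not say when the two periods fall.

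The Sub-hypothesis paragraph under Hypothesis 2 looks at improvement "at 12 months postpartum as compared to during pregnancy or immediately postpartum". It ties this back to the main models: "As such we repeated the analyses outlined in H1 and H2 specifically within each of the treatment arms".

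Stage comes up again under Additional analyses: "We will examine the impact of gestational age or length postpartum on EPDS score". The sentence that opens that section announces work on change in patient-level measures and on variation in the treatment effect.

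The general Analysis plan paragraph summarises every variable and adds: "Bivariate associations between explanatory variables of interest were assessed by student t-tests, Wilcoxon rank-sum, and Chi-square tests".

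**The concern.** Read together, these sections suggest that the earlier Hypothesis 1 assessment is taken in pregnancy for some patients and soon after birth for others. This is an inference, because the SAP does not define the two periods. EPDS may move differently from those two starting points up to 12 months postpartum. If PRISM clinics also enrolled a different share of pregnant patients than the comparison clinics, part of the group-by-period estimate would reflect who was enrolled and not what PRISM did. The stated model has no term to separate the two. The planned stage analysis names EPDS score and is not expressly linked to the group-by-period contrast. At stake is whether a reader can attribute an estimated difference to PRISM.

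**Working it through.** The 2 points are a target, not a derived figure, so there is nothing to reproduce. The SAP gives no sample size, SD, power, number of clinics, stage mix or change by stage. Every input below other than the 2 points is therefore an assumption.

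**1. When stage can enter the contrast.** Let p₁ and p₀ be the shares enrolled in pregnancy in PRISM and in the comparison arm. Let a and b be the expected EPDS changes for the two stages without PRISM, and θ the PRISM effect.

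- Mean change, PRISM: θ + p₁a + (1 − p₁)b
- Mean change, comparison: p₀a + (1 − p₀)b
- Difference: θ + (p₁ − p₀)(a − b)

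The shift is the product of the stage-mix gap d = p₁ − p₀ and the stage difference in change δ = a − b. It is zero if either is zero.

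**2. Check on noise-free data with a true contrast of 2.0 points** (size of the group-by-period estimate):

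| Stage mix by arm | δ | Stage difference in level | Stated model | Plus stage | Plus stage × period |
|---|---|---|---|---|---|
| 60% v 40% | 0 | 3 | 2.0 | 2.0 | 2.0 |
| 50% v 50% | 2 | 3 | 2.0 | 2.0 | 2.0 |
| 60% v 40% | 2 | 3 | 2.4 | 2.4 | 2.0 |
| 40% v 60% | 2 | 3 | 1.6 | 1.6 | 2.0 |

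The mechanism is real, needs both conditions, and can act in either direction. A stage difference in level alone does nothing.

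**3. How large a gap chance would produce.** Assume a 50/50 stage split, 30 patients per clinic, K clinics per arm and a stage ICC of 0 to 0.10:

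SD of d = √[2 × 0.25 / (30K) × (1 + 29 × ICC)]

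- Smallest case, K = 10, ICC = 0: √(0.5/300) = 0.041
- Largest case, K = 5, ICC = 0.10: √(0.5/150 × 3.9) = 0.114

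The median absolute gap is 0.674 × SD, which is 2.8 to 7.7 percentage points. With δ of 1 to 2 points, the shift runs from 0.0275 × 1 ≈ 0.03 to 0.077 × 2 ≈ 0.15 EPDS points. Divided by 2, that is 1% to 8% of the target.

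The probability of a gap above 10 points is 8% to 38% with 5 clinics per arm and 1% to 21% with 10. For a gap above 20 points it is at most 8% and 1.3%.

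**4. What this does to the confidence interval.** If the study had 80% or 90% power for 2 points, the SE would be 2/(1.96 + 0.842) = 0.714 or 2/(1.96 + 1.282) = 0.617. Averaged over chance gaps:

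coverage = 2Φ(1.96 / √[1 + (SD × δ / SE)²]) − 1

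- Best case (SD 0.041, δ = 1, SE 0.714): 95.0%
- Worst case (SD 0.114, δ = 2, SE 0.617): SD × δ / SE = 0.370, √1.137 = 1.066, 1.96/1.066 = 1.838, coverage 93.4%. With SE 0.714 it is 93.8%.

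This errs against the plan: it adds the stage variation on top of the SE, although differences in change between stages are part of the residual scatter from which the SE is estimated.

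**5. The two conditions against the text.** Nothing in the SAP indicates that stage mix differed by arm or that recruitment differed. Nothing gives EPDS change by stage. The general paragraph already summarises all variables, and its bivariate step can include stage by group. The additional analysis of stage sits in a section devoted to change and to variation in the effect, and its method is left open.

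**The case for a change.** The strongest reply is that a reader sees one realised estimate, not an average over chance. Given a 20-point gap and a 2-point stage difference in change, the shift is 0.2 × 2 = 0.4 points, 20% of the target, and coverage conditional on that gap falls to 91.3% (SE 0.714) or 90.1% (SE 0.617). The SAP does not state the allocation method, so randomisation cannot be taken for granted. The planned stage analysis does not mention the group-by-period term, and a stage main effect alone would leave the contrast unchanged in patients with both assessments. A model with stage by period would cost little: the CI would be about 0.5% to 2% wider at a 10- to 20-point gap if stage does not predict change.

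The algebra stands, and so does the remark that the SAP does not spell out how its stage analysis relates to Hypothesis 1. The rest does not make a defect. The 0.4-point case needs a gap with a chance probability of at most 8% together with the larger assumed stage difference. Anything bigger by way of systematic imbalance would need differential recruitment, of which the SAP shows no sign. Allocation, any stratification and the visit schedule commonly sit in the protocol, which is not at hand, so their absence here proves nothing. Since the SAP leaves the stage method open, it does not rule out an analysis of change or of effect by stage.

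**Conclusion.** The concern does not hold. The SAP states a legitimate unadjusted contrast, and no rule, number or analysis in it is shown to be wrong on this point. Stage can distort that contrast only when two conditions hold together, and the document supports neither. Under the assumed chance model the typical shift is about 0.03 to 0.15 EPDS points against a 2-point target, with average coverage of about 93.4% to 95.0%. What remains is at most a missing detail: how the planned stage analysis connects to Hypothesis 1. An extra model would be post hoc, since the SAP is dated 5/9/23 and describes the Hypothesis 1 analysis in the past tense, and it would leave the main result as it is.

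This rests on the assumed clinic numbers, cluster size, ICC, power and stage difference in change, and on recruitment not having differed by arm. Evidence of clearly different stage mixes in the two arms would reopen the question. Whether Hypothesis 1 accounts for clinic is a separate matter, not judged here.

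### The Hypothesis 1 model has no clinic term although the arm is set by clinic, so its p-value and 95% CI hold only if clinics do not differ in mean EPDS change beyond the arm effect

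*SAP*

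**What the plan says.** The hypothesis, under Data analysis Hypothesis 1 in the SAP, is that "Depressed perinatal patients receiving care from clinics enrolled in PRISM will experience more improvement in depression symptoms" than patients of the enhanced usual care clinics, with a target of a "2 point difference-of-difference in EPDS".

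For the analysis, "we used unadjusted repeated measures linear regression models with the EPDS score as the dependent variable". The predictors are the arm and "two time periods as the independent variables along with the interaction term of group by time period". The between-arm difference in change is given with a 95% CI and a p-value. No clinic effect, cluster-robust variance or clinic-level analysis is named.

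Under Data analysis Hypothesis 2, after the logistic regressions for treatment initiation and sustainment, the SAP adds: "These models were run both unadjusted and accounting for clustering of practices within treatment groups using Mixed Model analysis with clinic as a random effect".

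**The concern.** The arm is a property of the clinic, whatever the method by which clinics came to their arms. Women in one clinic share staff, practice and the way the programme was delivered, so their EPDS changes may be more alike than those of women from different clinics. A repeated-measures model deals with the correlation between the scores of one woman. It does not deal with correlation between women of the same clinic.

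The SAP recognises clustering and applies a remedy, but only to Hypothesis 2. If clinics differ in mean change for reasons unrelated to the arm, the Hypothesis 1 model counts women as independent when they are not. A chance difference between the clinics of the two arms can then be reported as an effect of PRISM on depression symptoms.

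**Working it through.** **Inputs from the SAP.** Arm defined by clinic; model terms arm, period and their interaction; 95% confidence, taken as a two-sided 5% test; target of 2 EPDS points. The SAP states no sample size, power, clinic count, SD or ICC, so there is no planned figure to reproduce. All values below for women per clinic (m), clinics per arm (k), SD of change and ICC of change are assumptions.

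**Step 1: what cancels.** Write a woman's score as arm and period effects + clinic level + clinic-by-period effect + woman effect + error. In her change, second score minus first, the clinic level and the woman effect drop out. The clinic-by-period effect stays, and all women of that clinic share it. In simulation (5 clinics per arm, 30 women each, both scores present) the patient-level test rejected a true null 4.7% of the time when clinics differed only in level. With a clinic effect on change it rejected 11.6% at ICC 0.02 and 20.7% at ICC 0.05.

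**Step 2: type I error of the model as written, equal clinics.** DEFF = 1 + (m − 1) × ICC, and type I error = 2 × [1 − Φ(1.96 / √DEFF)]. The clinic count does not enter.

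| ICC of change | m = 15: DEFF | Type I error | m = 30: DEFF | Type I error |
|---|---|---|---|---|
| 0 | 1.00 | 5.0% | 1.00 | 5.0% |
| 0.01 | 1.14 | 6.6% | 1.29 | 8.4% |
| 0.02 | 1.28 | 8.3% | 1.58 | 11.9% |
| 0.05 | 1.70 | 13.3% | 2.45 | about 21% |

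Example: m = 30 and ICC 0.05 give 1.96 / √2.45 = 1.252, hence 2 × [1 − Φ(1.252)] = 0.2105. The coverage of a nominal 95% CI is 100% minus the type I error, so it runs from about 93% down to 79% over the positive ICCs.

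**Step 3: unequal clinics.** With a coefficient of variation (CV) of clinic size, DEFF is approximately 1 + [(1 + CV²) × m − 1] × ICC. For m = 15, CV 0.45 and ICC 0.01 this is 1.17, a type I error of 7.0%. For m = 30, CV 0.60 and ICC 0.05 it is 2.99, or 25.7%. Simulation gave 7.0% to 25.9% over ICC 0.01 to 0.05.

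**Step 4: size in EPDS points.** Clinic variation alone moves the between-arm difference in change, as a 95% range, by ±1.96 × SD × √ICC × √(2/k). With SD of change 5 to 6:

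| Clinics per arm | ICC 0.01 | ICC 0.05 |
|---|---|---|
| 10 | ±0.44 to 0.53 | ±0.98 to 1.18 |
| 5 | ±0.62 to 0.74 | ±1.39 to 1.66 |
| 3 | ±0.80 to 0.96 | ±1.79 to 2.15 |

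The target is 2 points.

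**Step 5: do the alternatives hold 5%?** Simulation on change scores, 20,000 runs per setting; k = 2, 3, 5, 10; m = 15, 30; ICC 0 to 0.05.

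- Equal clinics: the t-test on clinic means and the bias-reduced cluster-robust test both rejected 4.7% to 5.3%.
- Unequal clinics: the t-test on clinic means rejected 3.5% to 5.2%. The cluster-robust test rejected 4.0% to 5.4% with 3 or more clinics per arm, and up to 6.3% with 2.

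**Step 6: would the Hypothesis 2 remedy do?** A clinic random intercept models a constant clinic level, which Step 1 shows has already cancelled. In 60 simulated data sets with two scores per woman (k = 5, m = 15, ICC 0.05), adding it moved the interaction statistic by at most 0.01.

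**The case against.** The strongest objection is about size. What matters is the ICC of change, not of EPDS level, and the SAP gives no basis for any value of it. At 0 there is no harm. At 0.01 with 15 women per clinic the error is 6.6%, which few would call serious. This stands: the document cannot show that the reported result is materially wrong. The finding rests on an assumption that the SAP neither states nor checks.

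Second, the SAP is a short account in the past tense, and a clustered Hypothesis 1 analysis may have been run and not described. The sentence on clustering speaks of mixed models and could be stretched to cover both hypotheses. But it sits in the Hypothesis 2 paragraph, follows the logistic models, and sets the unadjusted version against the clustered one. Unadjusted is the only version named for Hypothesis 1. If a clustered analysis exists, the document needs to say so.

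Third, the cancellation in Step 1 and the result in Step 6 are exact only when every woman has both scores, which the SAP does not say. This is correct but small. With an assumed 30% missing follow-up, two separate simulation checks found that the random intercept moved the statistic by 0.03 and 0.05 on average. It still does not repair the test.

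Last, the absence of the protocol is no answer, because the model and its inference are specified here.

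**Conclusion.** The point holds and has to be corrected. As written, the Hypothesis 1 p-value and 95% CI are valid only if clinics within an arm do not differ in mean EPDS change. The direction is certain: any positive clinic variation in change makes the test too liberal and the interval too narrow. The size is not known from this document. For ICCs of change from 0.01 to 0.05 and 15 to 30 women per clinic of equal size, the type I error would be 6.6% to about 21%. With few clinics, clinic variation alone could produce a between-arm difference close to the 2-point target. The within-arm sub-hypothesis and the choice between the two Hypothesis 2 models are not part of this finding.

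**What to change.** First state whether a clustered Hypothesis 1 analysis was already run. If not, re-analyse with a method that allows for clinic variation in change and takes its degrees of freedom from the number of clinics, and rest the conclusion on it. Acceptable methods:

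- **t-test on clinic mean EPDS change**, df = number of clinics − 2. This is the simplest.
- **Cluster-robust variance with a small-sample correction** (bias-reduced, Satterthwaite df), with 3 or more clinics per arm.
- **Mixed model with clinic and clinic-by-time random effects**, df = number of clinics − 2. It is conservative because the clinic-by-time variance is often estimated as zero. In the equal-clinic simulations it rejected 2.8% to 5.1% with 10 clinics per arm, 1.6% to 4.4% with 5, and 0.4% to 2.8% with 3.

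A clinic random intercept alone is not enough. Choose the method from the number and sizes of the clinics, not from its result. Report the number of clinics and the between-clinic SD of change, show the unclustered model beside it as a sensitivity analysis, and label the clustered analysis as added after the original one.

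**Cost.** No new data, since clinic is already modelled for Hypothesis 2; the work is a re-analysis and a corrected report. The interval may widen even if the ICC is 0. With equal clinics the factor is t(0.975, 2k − 2) / 1.96:

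| Clinics per arm | Calculation | Widening |
|---|---|---|
| 10 | 2.101 / 1.96 | 7% |
| 5 | 2.306 / 1.96 | 18% |
| 3 | 2.776 / 1.96 | 42% |
| 2 | 4.303 / 1.96 | 120% |

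Unweighted clinic means cost more than this when clinic sizes are unequal. With 2 or 3 clinics per arm the interval may be too wide to judge a 2-point difference, and the report would have to say so.

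### The SAP gives two unreconciled definitions of the Hypothesis 2 primary outcome and does not say how its three analysed variables decide the hypothesis

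*SAP*

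**What the plan says.** Both definitions stand in the SAP under Data analysis Hypothesis 2.

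- **The hypothesis.** Initiation is defined "as measured by attendance and one initial mental health assessment or treatment visit". Sustainment is "an average ≥ 1 mental health visit every 1 months until remission of symptoms or study assessment". Only mental health visits enter.
- **The analysis text that follows.** "Our primary outcome in this hypothesis was treatment initiation and sustainment", in the singular, "which was operationalized as receipt of prescription by an obstetrician, attendance in mental health visit(s), and adherence to medication". On the scale of these three variables the text then adds: "all of which were represented as dichotomous variables".
- **The model.** Logistic regression is used "to determine the impact of treatment group (PRISM/MCPAP) on treatment initiation and sustainment", with odds ratios, confidence intervals and p-values. "These models were run both unadjusted and accounting for clustering of practices within treatment groups", the latter with clinic as a random effect.

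The section gives no significance level, no decision rule and no adjustment for multiple tests. It points to no other document for them. Both main analyses are described in the past tense.

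**The concern.** The two statements describe one outcome but do not have the same content. Two of the three analysed variables concern medication, which the hypothesis does not mention. The hypothesis's frequency criterion and its end at remission do not appear in the analysis text.

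Two things are at stake. First, a conclusion that PRISM improved sustained mental health attendance would not be shown to rest on the analysis described. Second, if the three variables disagree, the plan gives no overall verdict on Hypothesis 2. Each odds ratio could still be read on its own, but nothing says which one, or which combination, answers the question posed.

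**Working it through.** The SAP states no power, sample size or significance level for Hypothesis 2, so there is no figure of its own to reproduce. The check is mainly a comparison of the two statements.

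**1. The definitions side by side**

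| Element | Hypothesis | Analysis text |
|---|---|---|
| Initial mental health visit | Required | Attendance, no threshold given |
| Average of at least one visit a month | Required | Not mentioned |
| Window ending at remission or study assessment | Stated | Not mentioned |
| Obstetrician prescription | Not mentioned | One of three variables |
| Medication adherence | Not mentioned | One of three variables |

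The overlap is visit attendance only.

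**2. Do the definitions classify patients differently?** Taken as worded, they can.
- A patient treated only through an obstetrician's prescription, and adherent, scores on two of the three analysed variables but fails the hypothesis definition, having had no mental health visit.
- A patient with a single visit over many months could count as attending, since no threshold is given, but fails the monthly average.

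**3. How many results?** The text does not settle this.
- If the variables were modelled separately, which is the likelier reading, there are 3 variables × 2 models (unadjusted; clinic as random effect) = 6 odds ratios.
- If they were combined into one binary, there are 2 odds ratios, and the text does not say whether any or all of the components were required.

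In neither case is one result named as decisive.

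**4. How much could the missing rule matter?** This is illustration only. Assumptions: three separate tests, each two-sided at 5% and holding that size; PRISM has no effect on any of the three; equal correlation between the test statistics.
- Any one counts, independent tests: 1 − (1 − 0.05)³ = 1 − 0.857375 = 0.1426.
- All three needed, independent tests: 0.05³ = 0.000125.
- At correlation 0.5 (simulation, 1,000,000 draws): 0.125 for any and 0.003 for all.

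| Rule | Correlation 0 | Correlation 0.5 |
|---|---|---|
| Any one of three | 14.3% | 12.5% |
| All three | 0.01% | 0.3% |
| One pre-defined outcome | 5% | 5% |

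The rule matters for power too. With an assumed 80% power for each variable, the chance of meeting the any rule is 99% at correlation 0 and 95% at 0.5. For the all rule it is 51% and 61%.

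**5. Contrast with Hypothesis 1.** The hypothesis is framed on the EPDS and the analysis uses "repeated measures linear regression models with the EPDS score as the dependent variable". Hypothesis and model name the same outcome, so this problem does not arise there.

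**The case against.** The strongest reply is that the two statements can be made compatible. They overlap on mental health visits. The dichotomous attendance variable could be shorthand for the hypothesis's visit criteria, since the analysis text offers no other threshold. Prescription and adherence could be a deliberate broadening, standing for initiation and sustainment of medication. This is fair, and it means that a reader should not infer a flat contradiction, or that visit-based sustainment was certainly left untested. What remains is that the SAP says neither thing. A protocol that is not shown might explain the choice, but both statements stand in this document and nothing in it links them.

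A second reply is that six p-values and an inflated error rate are not facts about this plan. That is right. A reader might infer both from the plural reference to models, but that plural could mean two versions of one composite model. An any-one-counts rule appears nowhere, and an all-three rule, equally unstated, would be conservative in the case calculated. The percentages show only how much depends on an unstated rule.

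A third reply is that the analyses have been run, so no pre-specified rule can be restored. This limits the remedy to disclosure and labelled re-analysis. It does not remove the need to say what was tested.

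**Conclusion.** The point holds as a mismatch within the SAP's own text. The outcome it calls primary for Hypothesis 2 has two unreconciled definitions, and these can classify the same patient differently. Following the plan as written does not show that sustained visit attendance was tested. It is also not stated whether the three variables form a composite or stand alone, or which result decides the hypothesis.

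This rests on the text alone and needs none of the assumed figures. The range in the illustration, from about 14% down to about 0.01%, depends wholly on the assumed level, correlations and rule, and is not an estimate of this trial's error rate.

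A reader might go further and infer that mixed results could say nothing about Hypothesis 2, or that the investigators would take any favourable variable as support. The SAP supports neither inference: separate odds ratios with intervals remain interpretable one by one, and the second reading argues from silence.

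**What to change.** 1. Reconcile the two statements. Say which outcome was pre-specified for Hypothesis 2 and cite the dated document that fixed it. If attendance was shorthand for the visit criteria, or the medication variables a deliberate broadening, say so and give the threshold used.
2. Where visit and remission data exist, derive and report the visit-based binary that the hypothesis defines. Label it a post hoc re-analysis, and note that its window ends at remission, which treatment may itself affect.
3. State whether the three variables were analysed as a composite (any or all) or separately. If separately, report each as secondary or under a disclosed decision rule. If any one result can support the hypothesis, adjust for multiplicity, for example by Holm, where at an assumed overall 5% the smallest p-value is compared with 0.05/3 = 0.0167.
4. If the visit-based outcome cannot be derived, state that Hypothesis 2 as worded was not tested, and limit each conclusion to the variable analysed.

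The cost is a wording change and a disclosure and, where the data exist, one derived variable and a small rerun of the Hypothesis 2 models. The drawback is that any rule fixed now is post hoc and must be disclosed as such. Nothing changes for Hypothesis 1.

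### As written, the H2 logistic models hold no earlier treatment status or time term, although H1 has one and the sub-hypothesis implies one for H2

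*SAP*

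**What the plan says.** In the SAP under Data analysis Hypothesis 2, the claim to be tested is that "clinics enrolled in PRISM will have improved treatment initiation and sustainment". The outcome is "operationalized as receipt of prescription by an obstetrician, attendance in mental health visit(s), and adherence to medication, all of which were represented as dichotomous variables". Nothing in that sentence requires the treatment to be new since entry. The analysis sentence, which also covers sustainment, is "we used logistic regression to calculate odds ratios, corresponding confidence intervals and p-values to determine the impact of treatment group (PRISM/MCPAP) on treatment initiation". The models were "run both unadjusted and accounting for clustering of practices within treatment groups using Mixed Model analysis with clinic as a random effect". Group is the only fixed effect named. No time period, interaction or participation status at an earlier assessment appears.

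Under Data analysis Hypothesis 1, the EPDS model has group and "two time periods as the independent variables along with the interaction term of group by time period", so the earlier score is used.

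The sub-hypothesis expects some "improvement in depression and treatment participation at 12 months postpartum as compared to during pregnancy or immediately postpartum" in the enhanced usual care arm. It then says that the H1 and H2 analyses were rerun inside each arm, where the time effect alone was examined in place of an interaction between treatment and time. That wording presupposes that both between-arm analyses, H2 included, had such an interaction.

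**The concern.** H2 is partly about starting treatment, and its population is described as depressed perinatal patients, not as untreated ones. If a woman who already attends mental health visits or takes medication at entry scores yes on a component, that yes says nothing about what the programme started. A group-only model cannot tell her from a woman who newly began.

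Two consequences follow if such women are present. If the arms differ in the share already treated, the difference goes straight into the odds ratio and can create or hide an effect. If the shares are equal, there is no false effect, but the contrast in new initiation is diluted.

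The SAP removes entry differences in H1, and its sub-hypothesis treats participation at an earlier period as known. The information therefore appears to be available, yet the H2 paragraph does not use it. Because the sub-hypothesis points the other way, a reader cannot tell which model produced the H2 odds ratios.

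**Working it through.** **Step 1. The passages side by side.**

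| Place in SAP | Fixed effects | Earlier value used? |
|---|---|---|
| H1 | group, time, group-by-time | yes |
| H2 paragraph | group | no |
| H2 as the sub-hypothesis implies it | interaction of treatment with time | yes |

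The second and third rows cannot both describe the H2 analysis.

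**Step 2. Formula.** The SAP gives no event rate, sample size or number of clinics for H2, so there is no stated figure to reproduce and every input below is an assumption. Let b be the share already in treatment at entry, s the share of those who count as events, and q the share of untreated women who newly start. Then

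P(event) = b·s + (1 − b)·q, and OR = odds(PRISM) / odds(usual care).

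**Step 3. Imbalance, no true effect** (q and s equal in both arms; q from 0.2 to 0.4, s from 0.8 to 1.0).

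- Upper end for 20% prior treatment in usual care and 30% in PRISM, with q = 0.2 and s = 1: 0.20 + 0.80 × 0.2 = 0.36 against 0.30 + 0.70 × 0.2 = 0.44. OR = (0.44/0.56) / (0.36/0.64) = 1.40.
- Lower end, with q = 0.4 and s = 0.8: 0.16 + 0.32 = 0.48 against 0.24 + 0.28 = 0.52. OR = 1.17.
- Imbalance reversed: 0.72 to 0.85.
- 20% against 40%: 1.38 to 1.93; reversed, 0.52 to 0.73.
- Equal shares, or nobody in treatment at entry: 1.00.

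**Step 4. Dilution, equal prior treatment, s = 1.** Take a true OR of 2.0 for new initiation.

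- q = 0.2 against 0.333 with b = 0.4: 0.52 against 0.60, OR 1.38.
- q = 0.4 against 0.571 with b = 0.2: 0.52 against 0.657, OR 1.77.

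The range for b from 20% to 40% is 1.38 to 1.77.

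**Step 5. Chance imbalance between clinics.** Assume no true effect, prior treatment averaging 30%, q = 0.3 and s = 1. Simulated clinic-level rates give the following 95% ranges of the OR from imbalance in prior treatment alone.

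| Clinics per arm (assumed) | Between-clinic SD 5 points | SD 15 points |
|---|---|---|
| 5 | 0.84 to 1.19 | 0.60 to 1.67 |
| 10 | 0.88 to 1.13 | 0.69 to 1.44 |

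A clinic random effect reflects this variation in the width of the interval. It does not move the estimate back to 1.00.

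**Step 6. Effect of the covariate.** Within each level of entry status, Step 3 compares s with s or q with q, so the OR given entry status is 1.00 whatever the imbalance.

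**The case against.** Several points against the concern have force.

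- **H2 may already have a time term.** The sub-hypothesis implies it. A reader might infer from the H2 paragraph that earlier participation was ignored, but the SAP read as a whole does not settle that. What it establishes is a contradiction about the model. This stands.
- **Already-treated women may not be in the data, or may not score.** A reader might also infer that they count as having initiated. That needs them to be eligible and the outcome window to admit earlier care. The SAP states neither, and both are commonly left to the protocol. One component counts only a prescription from an obstetrician, and the hypothesis speaks of an initial visit, which leans towards new care. This stands: the problem is conditional.
- **Comparing participation among all patients is a legitimate target.** For a clinic-level programme it is, and sustained visits and adherence can improve in women already treated. Dilution is then a feature of the target and not a bias, and restricting to untreated women changes the question. This stands, which is why restriction belongs in a sensitivity analysis.
- **The clinic random effect covers chance differences between clinics.** It does so in the interval, but it does not remove an imbalance between arms from the estimate. This stands only in part.
- **The sizes are all assumed.** They are, and s = 1, which counts every previously treated woman as an event, is the extreme case. Step 3 also shows s = 0.8.

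**Conclusion.** The point holds in a conditional form. The H2 paragraph specifies group as the only fixed effect and no use of earlier participation, while the sub-hypothesis implies a treatment-by-time interaction. The SAP contradicts itself on the model behind its H2 odds ratios.

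Whether the odds ratio is distorted depends on two facts the SAP does not give: whether some women were in treatment at entry, and whether the arms differed in that share. If nobody was, there is no distortion. If some were and the arms were balanced, the null value stays at 1.00 and a true effect is diluted. Only an imbalance can create a spurious effect. The documents therefore do not support saying that the H2 result is biased. The ranges in the working show what plausible rates would do; they do not estimate what happened. The change is still worth making, because it uses a value the SAP appears to have and removes an entry difference that the clinic random effect leaves in place.

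**What to change.** 1. Reconcile the H2 paragraph with the sub-hypothesis and state which model was fitted.
2. In the clinic-random-effect H2 models, include participation at the first assessment as a covariate. Alternatively, state the group-by-time model explicitly. The two estimate different quantities, and initiation has no obvious value at the first time point, so one should be named as the main analysis.
3. Report initiation among women not in treatment at the first assessment as a sensitivity analysis.
4. Keep the present group-only model as secondary, so that the effect of the change is visible.

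The cost is SAP wording and a rerun on data the SAP implies were collected. The main models gain one term, and the restricted analysis has a smaller sample. Two cautions apply. The adjusted odds ratio is conditional on entry status, so it need not equal the group-only one even with balance. If nearly all women in treatment at the first assessment count as events, the covariate's coefficient may be unstable and the arm effect will rest mainly on the untreated women.
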